Investigators and clinical trial site staff who are responsible for the conduct, management, or oversight of NIH-funded clinical trials have completed Human Subjects Protection and ICH GCP Training.

1 PROTOCOL SUMMARY

1.1 SYNOPSIS

Title:	Postpartum dysglycemia screening with continuous glucose monitoring
Study	Gestational diabetes (GDM) is one of the most common complications of pregnancy, and up to one third of women with GDM will have abnormal blood sugars after their pregnancy. To screen for abnormal blood sugars, standard of care is a 6-12 week postpartum oral glucose tolerance test (OGTT). However only 17-60% of women actually have this test performed. This study is to assess the feasibility of using a continuous glucose monitor placed on discharge from the hospital after delivery as a screening method to detect postpartum abnormal blood sugars.
Description:	
Objectives:	
Primary Objective: To assess the feasibility of continuous glucose monitoring compared to oral glucose tolerance testing for the diagnosis of postpartum diabetes in women with recent gestational diabetes.
 
Secondary Objectives: To evaluate the specificity, sensitivity, positive predictive value, and negative predictive value of continuous glucose monitoring compared to oral glucose tolerance testing for the diagnosis of postpartum dysglycemia in women with recent gestational diabetes.
 
To evaluate the influence of predictors of lack of postpartum oral glucose tolerance testing on completion of postpartum continuous glucose monitoring.

Endpoints:	
Primary Endpoint: Percentage of participants with at least 72 hours of CGM data downloaded.
 
Secondary Endpoints: CGM acceptability scoring Specificity, sensitivity, PPV, and NPV for CGM compared to OGTT will be performed for diagnosis of DM, IGT, and IFG

Study Population:	Pregnant or recently pregnant women who were diagnosed with GDM during current/recent pregnancy. Target enrollment: 50 participants
Sites/Facilities Enrolling Participants:	Icahn School of Medicine at Mount Sinai

[figure not shown]

Description of Study Intervention: Women will be consented and screened before or after delivery. They will be asked about medical history, medications, and diabetes risk factors. A Dexcom Professional CGM will be placed on postpartum day 1-3. Participants will wear the sensor for 10 days and return it at their postpartum visit or by mail. They will be given another sensor to place before their standard of care OGTT and will mail the sensor back after that test is performed.

Study Duration: 1 years

Participant Duration: Up to 20 weeks

1.2 SCHEMA

1.3 SCHEDULE OF ACTIVITIES (SOA)

Visit	1	2	3	4	Home	5
Timing	Third trimester or 1-3 days postpartum	1-3 days postpartum	1-4 weeks postpartum	4-12 weeks postpartum	4-12 weeks postpartum 2-5 days before OGTT	4-12 weeks postpartum
Setting	In person or telehealth	Postpartum floor or telehealth	In person or telehealth	Telehealth		Telehealth or in person
Consent	X					
Medical history	X					
Pregnancy/Fetal outcome questions	X	X				
Professional sensor training	X	X		X		

Sensor placement		X			X	
Return of sensor			X			X
Skin assessment			X			X
Questionnaire			X			X
OGTT reminder call				X		

2 INTRODUCTION

2.1 STUDY RATIONALE

Gestational diabetes (GDM) is one of the most common complications of pregnancy. Up to one third of women with GDM will have persistently abnormal blood sugars postpartum, and up to 70% will develop diabetes later in life. In order to diagnose persistent postpartum dysglycemia and future risk of type 2 diabetes, the American Diabetes Association (ADA), American College of Obstetrics and Gynecology (ACOG), and World Health Organization (WHO) recommend that all women with GDM undergo an oral glucose tolerance test (OGTT) at 6-12 weeks postpartum [1-3]. However, this screening occurs in less than half of women diagnosed with GDM. Thus, standard of care for screening for postpartum dysglycemia is not occurring for the majority of women. A more feasible and convenient alternative for screening is needed. This study aims to assess the feasibility of continuous glucose monitoring (CGM) compared to OGTT for the diagnosis of postpartum dysglycemia in women with recent GDM.

2.2 BACKGROUND

Though considered the standard of care, postpartum OGTT screening for women with GDM is not performed in the majority of women. Previous research has tried to address promotion and incentivizing of OGTT testing, but has only achieved screening rates of up to 60% [5].

Alternative testing strategies have failed to achieve the desired feasibility and predictive value needed. The goal of this study is to assess the feasibility of a postpartum 10 day CGM study for detection of postpartum diabetes, impaired glucose tolerance (IGT), and impaired fasting glucose (IFG). CGM will be placed on discharge from the hospital and worn for 10 days. CGM will be returned at approximately 2 weeks postpartum at routine obstetrics or pediatric visits, or by mail. Postpartum CGM has the potential to greatly increase adherence rates to postpartum testing compared to 6-12 week OGTT. The secondary objectives of this study are to assess the sensitivity and specificity of postpartum CGM compared to standard of care OGTT and to assess for predictors of non-completion.

GDM is common and is a risk factor for future dysglycemia. GDM complicates 7% of pregnancies and is one of the most common complications of pregnancy [2]. Though for many women GDM resolves at delivery, up to one third of women with GDM will have diabetes or IGT at postpartum screening, and up to 70% will develop diabetes later in life [2]. Early diagnosis of dysglycemia allows early interventions which have been shown to decrease the risk of progression from IGT to diabetes, including weight loss, physical activity, breastfeeding, and pharmacologic interventions [6]. Postpartum screening can also be an opportunity to optimize health before future pregnancies to decrease the risk of maternal and fetal complications in addition to the long term risks of diabetes. Newly discovered, previously undiagnosed type 2 diabetes is associated with previous history of GDM, and is associated with increased perinatal risks when compared with GDM including perinatal mortality (OR 2.3), preterm birth (OR 2.6), congenital anomalies (OR 2.1), neonatal intensive care unit admission (OR 3.1) and neonatal hypoglycemia (OR 406) [7].

Standard of care for postpartum screening is not met by the majority of women who are at high risk to continue to have dysglycemia. Screening for diabetes and IGT using a 75-g, 2 hour OGTT is recommended by obstetric and endocrinology societies including ADA, ACOG, and WHO at 6-12 weeks postpartum [1-3, 8]. Unfortunately, postpartum screening at this time only occurs in 17-60% of women even during studies designed to promote testing [9-11]. In a randomized control trial, Clark et al found that postal reminders to patients and physicians led to an increase in screening by one year postpartum with 14.3% tested by one year with no reminder, 51.6% with a reminder to the physician, 55.3% with reminder to patient, and 60.5% with reminder to physician and patient ($p<0.05$) [5]. Implementation of this strategy at two Canadian hospital systems did increase rates of screening, but not as robustly as seen in the original randomized control trial described above [9], with 28% OGTT completion by 6 months with reminders compared with 14% completion with usual care ($p=0.1$) [12]. The DIAMIND study in Australia found that a reminder at six weeks did not increase screening by six months postpartum [13]. Multiple interventions have been studied at Mount Sinai Hospital: after implementation of an advanced order set at the 35-week pregnancy visit, provider education modules, and nutritionist phone calls reminding patients to fast before postpartum testing, OGTT test completion in association with a six week postpartum visit increased from 17% to 36% ($p=0.01$) [10].

Increased interaction with a healthcare system and health literacy are associated with higher likelihood of postpartum testing [9, 11]. The strongest predictor of effective postpartum diabetes screening is attendance at postpartum healthcare visits [9]. The influence of race and ethnicity on postpartum screening rates is not consistent across studies [14], but in general there are strong associations of poor postpartum screening compliance with minority race, ethnicity, younger age, mental health disorders, and lower health literacy [11]. These disparities contribute to higher rates of undiagnosed diabetes in these populations which will have long term consequences on the women and their communities. During the COVID-19 pandemic, screening recommendations and adherence rates have changed further. For example, in the United Kingdom, Canada, and Australia, alternative and less testing have been recommended [15]. In the United States, no change in guidelines has been formally proposed; if it were, it could be expected to lead to further declines in postpartum screening, as women with lower health literacy and less access to healthcare having poorer follow up.

Alternative testing has not been able to replace postpartum OGTT. In theory, simpler screening tests might be considered, but these have proven inferior to the OGTT for postpartum dysglycemia screening. For example, fasting glucose values alone fail to capture some women with IGT and diabetes. A meta-analysis found a fasting glucose had a sensitivity of 16-89% compared to OGTT (the best sensitivity was a study performed 4-8 years after delivery) [16].

Hemoglobin A1C (HbA1C) measurements might seem a reasonable surrogate screening tool, but HbA1C can be lowered by increased red blood cell turnover during recent pregnancy and peripartum blood loss [3, 17]. One year after delivery, HbA1C compared to an OGTT has a reported sensitivity of 22.64% and PPV of 54.55% [17].

Multiple strategies have been explored to address this challenge. The selection of 6-12 weeks postpartum for the standard of care OGTT is mostly historical based on assumptions of changes in hormonal activity. However, markers of insulin sensitivity and production have been found to improve by postpartum days 1-5 (median day tested: postpartum day 2) [18]. The authors of that study concluded that the majority of improvements in metabolism occur in the immediate postpartum period [18]. An analysis of multiple studies looking at the accuracy of immediate postpartum OGTT before hospital discharge found good specificity (95.7%) and negative predictive value (NPV) (98.1%) for diabetes diagnosis, but performed sub-optimally when IFG and IGT were included (specificity 50.5%, NPV 75.3%) [19]. For women who receive steroids before or during labor, the impact on blood glucose levels would still be present on hospital day 2, so postpartum days 3-10 would likely perform better.

CGM for screening for dysglycemia in other populations. Chen et al found a strong correlation between CGM values and venous blood values during OGTT testing in otherwise healthy participants with fasting blood glucoses between 70-200 mg/dL [20]. In other populations where HbA1C cannot be depended on for diabetes diagnosis, such as thalassemia, use of CGM for diagnosis has been studied [21]. CGM detected more IGT and diabetes than OGTT in a study of cystic fibrosis patients [22].

CGM metrics in healthy volunteers have been established. Analysis of CGM in participants without diabetes has found very low percentages of time above 180mg/dL (median 0%, IQR 0-0.2%), above 160mg/dL (median 0.3%, IQR 0.1-0.9%), and above 140 mg/dL (median 2.1%, IQR 0.9-3.9%) [23]. Overnight monitoring, defined as midnight to 5:59am, the rates of time above these thresholds were even lower (IQR ranges 0-0%, 0-0%, and 0-1%, respectively), and time spent in the range 70-120mg/dL was 94% (IQR 88-97%) [23].

2.3 RISK/BENEFIT ASSESSMENT

2.3.1 KNOWN POTENTIAL RISKS

Participants using the CGM will be at low risk for developing a local skin infection at the site of the sensor needle placement. If a catheter is left under the skin for more than 24 hours it is possible to get an infection where it goes into the skin, with swelling, redness and pain. There may be bleeding where the catheter is put in and bleeding under the skin causes a bruise (1 in 10 risk). In less than 1 out of 500 participants the CGM might break and leave a small portion of the sensor under the skin that may cause redness, swelling or pain at the insertion site.

Some participants may develop skin irritation or allergic reactions to the adhesives used to secure the CGM. If these reactions occur, different adhesives or "under-taping" (such as with IV 3000, Tegaderm, etc.) will be tried, sites will be rotated frequently, and a mild topical steroid cream or other medication may be required.

Whenever the skin is broken there is the possibility of an infection. The CGM sensors are inserted under the skin. It is possible that any part that is inserted under the skin may cause an infection. These occur very infrequently, but, if an infection was to occur, oral and/or topical antibiotics can be used.

Data downloaded from the CGM will be collected for the study as measures of diabetes self-management behaviors. Some people may be uncomfortable with the researchers' having such detailed information about their daily diabetes habits.

Loss of confidentiality is a potential risk; however, standard operating procedures will be followed as detailed in section 9.1.2 to minimize this risk.

2.3.2 KNOWN POTENTIAL BENEFITS

This study is not designed with the purpose of providing personal direct benefit to the participants. CGM data can be shared with the participant or their providers after their OGTT at the participant's request which could provide benefit to the participant.

It is expected that this protocol will yield increased knowledge about the feasibility of using CGM as a screening tool for DM after GDM. If this is feasible, screening could increase in frequency and ease.

3 OBJECTIVES AND ENDPOINTS

OBJECTIVES	ENDPOINTS	JUSTIFICATION FOR ENDPOINTS
Primary To assess the feasibility of continuous glucose monitoring compared to oral glucose tolerance testing for the diagnosis of postpartum diabetes in women with recent gestational diabetes.	Percentage of participants with at least 72 hours of CGM data downloaded.	72 hours of data has been accepted as sufficient for identifying CGM trends
Secondary To evaluate the specificity, sensitivity, positive predictive value, and negative predictive value of continuous glucose monitoring compared to oral glucose tolerance testing for the diagnosis of postpartum dysglycemia in women with recent gestational diabetes.	CGM acceptability scoring Specificity, sensitivity, PPV, and NPV for CGM compared to OGTT will be performed for diagnosis of DM, IGT, and IFG	Of participants who receive standard of care, the CGM data will be compared to the standard of care to assess specificity, sensitivity, PPV, and NPV
Tertiary/Exploratory Association of risk factors with nonadherence to postpartum OGTT. A secondary analysis will be performed in which we remove any data within 4 half-lives of last known steroid exposure. Sensitivity and specificity of DM, IGT, and IFG for sensor worn at the time of postpartum OGTT will be explored.	Demographics, CGM return, OGTT completion Specificity, sensitivity, PPV, and NPV for CGM compared to OGTT will be performed for diagnosis of DM, IGT, and IFG excluding data within 4 half-lives of last known steroid exposure. CGM data from 4-12 weeks postpartum will be compared to the immediate postpartum CGM data and to the postpartum OGTT.	Demographic data will be analyzed to assess if similar populations complete CGM vs OGTT Steroids affect blood sugar. This exploratory analysis will help to determine if this needs to be considered when using CGM to assess for postpartum dysglycemia. Stability of CGM trends over the postpartum weeks will be assessed, and CGM data from the same time as OGTT will be compared.

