5.6 STRATEGIES FOR RECRUITMENT AND RETENTION

Since up to 40% of women do not attend any postpartum visits [11], our study recruitment and retention will need to be optimized. Participants will be recruited from their routine obstetrics and endocrinology visits and also from the postpartum labor and delivery floor. Consent will be translated into Spanish, and interpreters will be used to increase potential recruitment and recruit a more diverse and representative study population. We believe the availability of remote visits will decrease burden on participants, will increase retention for women who do not wish attend postpartum visits, and will address potential limitations on research visits at study sites due to COVID-19 concerns. The option for visit 2 to be performed either on the postpartum floor or remotely will allow recruitment of women who are delivering at multiple locations.

Compensation will be provided for time and effort. Participants will receive \$25 after Visit 1, \$75 after Visit 3 and an additional \$125 after completion of their standard OGTT. We estimate that 50% of participants will complete their standard OGTT with reminders and incentives; the enrollment goals have been planned accordingly.

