6.3 LOST TO FOLLOW-UP

Based on previous literature, we estimate that 50% of participants will complete their standard OGTT with reminders and incentives; the enrollment goals have been planned accordingly.

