8.2.4 EXPLORATORY ANALYSES

A secondary analysis will be performed in which we remove any data within 4 half-lives of last known steroid exposure.

CGM data from 4-12 weeks postpartum will be compared to the immediate postpartum CGM data and to the postpartum OGTT.

Sensitivity and specificity of DM, IGT, and IFG for sensor worn at the time of postpartum OGTT will be explored.

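### The steroid question is read only from whole-group accuracy in OGTT completers, which dilutes any effect in exposed women; a within-woman reclassification count in all exposed women would answer it more directly

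*Combined protocol and SAP*

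**What the plan says.** Section 8.2.4 states the analysis in one sentence: "A secondary analysis will be performed in which we remove any data within 4 half-lives of last known steroid exposure". The Section 3 table names its endpoint as specificity, sensitivity, PPV and NPV against OGTT "for diagnosis of DM, IGT, and IFG excluding data within 4 half-lives of last known steroid exposure", and its purpose as "This exploratory analysis will help to determine if this needs to be considered when using CGM to assess for postpartum dysglycemia".

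The accuracy comparison is limited to women who have the reference test: "Of participants who receive standard of care, the CGM data will be compared to the standard of care". Section 6.3 expects half to have it: "we estimate that 50% of participants will complete their standard OGTT with reminders and incentives".

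Steroid administration in the week before Visit 2 is recorded (Section 4.1, Visit 2), so exposed women can be identified. The documents give no expected number of exposed women, no analysis confined to them, no interval, and no rule for what would count as a change. Section 5.5 adds that a participant who meets an exclusion criterion after enrolment is left out of the analysis, and gives steroid use as the example.

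**The concern.** The question is whether steroids alter what CGM says about a woman. The planned readout approaches it indirectly, for two reasons.

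First, a woman with no steroid exposure has the same data, and so the same CGM category, in both versions of the accuracy table. She adds to the denominators but cannot contribute to a change. The whole-group change is the effect in exposed women multiplied by the exposed share.

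Second, accuracy requires an OGTT, but reclassification does not. Whether removing the window changes a woman's category can be seen from her sensor record alone. Exposed women who skip the OGTT are informative and are not used.

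At stake is what the pilot can hand on. The protocol itself holds that steroids affect blood sugar (Section 3) and uses their influence to argue for the timing of CGM (Sections 2.2 and 4.1). If the recomputed table barely moves, that says little about the size of the effect in exposed women, and the plan supplies no other result from which to judge it.

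**Working it through.** **Inputs from the documents.**
- Enrolment: 50 ("Target enrollment: 50 participants", Section 1.1).
- OGTT completion: 50% (Sections 5.6 and 6.3).
- Dysglycemia: Section 2.2 says "up to one third of women with GDM will have diabetes or IGT at postpartum screening". Taking the upper figure leaves two thirds non-dysglycemic.

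**Assumptions, not in the documents.** Exposed share e = 10%, 20% or 40%. Correction rate r = 50%: removing the window corrects a false-positive CGM category in half of exposed non-dysglycemic women. Exposure is taken as unrelated to OGTT completion and to dysglycemia.

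**The plan's own figure.** The target of 50 rests on earlier feasibility studies (Section 8.1), with no formula to reproduce. The number of OGTT completers follows as 50 × 0.50 = 25, of whom 25 × 2/3 ≈ 17 are non-dysglycemic.

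**Dilution.** Shift in overall specificity = e × r. The probability that a given completer changes is q = e × 2/3 × r. Expected changes = 25q. Chance that no category changes = (1 − q)^25.

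| Exposed share e | Exposed completers (25e) | Specificity shift (e × 0.5) | q | Expected changes (25q) | Chance of no change |
|---|---|---|---|---|---|
| 10% | 2.5 | 5 points | 0.033 | 0.8 | 43% |
| 20% | 5 | 10 points | 0.067 | 1.7 | 18% |
| 40% | 10 | 20 points | 0.133 | 3.3 | 3% |

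The effect in exposed non-dysglycemic women is 50 points in every row.

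**A smaller effect.** With r = 20%, q is 0.0133, 0.0267 and 0.0533. The shift is 2, 4 and 8 points, and the chance of no change is 71%, 51% and 25%.

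**What a within-woman count could use.** Exposed women among all 50 number at most 50e = 5, 10 or 20, against 2.5, 5 or 10 among completers. These are ceilings: some women will lack usable sensor data, and for some the window will have ended before the sensor was placed.

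**Precision of a null result.** If none of n exposed women is reclassified, the upper limit of the exact two-sided 95% interval is 1 − 0.025^(1/n). For n = 5 this is 52%; for n = 10 it is 31%.

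**The case against.** This is an exploratory analysis in a pilot, and the text says only that it will help to decide. Accuracy with and without window data, over everyone screened, is a legitimate quantity: it shows how much steroid exposure matters to CGM as a screen in that population. A 10-point shift would be visible in a descriptive table. The proposed count would not settle the matter either, since 0 of 10 still allows 31%.

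Much of this stands. The accuracy table deserves to stay, and the pilot will leave the question open. But population impact and effect in exposed women are different quantities. Only the first is planned, and it depends on an exposed share that the plan does not ask to be reported.

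A reader might go further and infer that an unchanged table is almost guaranteed. The figures do not support that: at 20% exposure and r = 50%, something changes 82% of the time (100% − 18%). A near-certain miss appears only if a significance test is imposed. An exact McNemar test needs six one-way changes (2 × 0.5^6 = 0.031; five give 0.0625), and with q = 0.067 the chance of six or more among 25 is about 0.5%. No such test is planned.

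A reader might also infer that the plan would treat no change as licence to ignore steroids. Nothing in the documents says so. Nor do they say that exposed women will be few.

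**Conclusion.** The point holds as a weakness of the readout. Whole-group accuracy among about 25 OGTT completers shows the effect in exposed women only after scaling by the exposed share, and it sets aside exposed women who have no OGTT. A small or absent change would therefore be weak evidence that steroids do not matter.

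The dilution itself is arithmetic and needs no assumption. Its size does. Under 10% to 40% exposure, a 50-point effect becomes a 5- to 20-point shift in specificity, and the chance that nothing moves ranges from 43% down to 3%. Those figures rest on an assumed exposure rate, an assumed correction rate, and the upper prevalence figure in Section 2.2.

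**What to change.** In Section 3 and Section 8.2.4:

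1. Make the main steroid readout a within-woman cross-tabulation: CGM category from all data against category with the steroid window removed. Use the categories of Section 8.2.2. Include every steroid-exposed woman with usable first-sensor data, whether or not she had an OGTT.
2. Report the number exposed, the number whose window overlaps sensor data, and the number reclassified, with an exact 95% confidence interval. A woman whose window ended before her sensor started cannot be reclassified and should be counted separately.
3. Keep the recomputed sensitivity, specificity, PPV and NPV as description, and state that an unchanged table will not by itself be taken to show that steroid exposure can be ignored.
4. Reconcile Section 5.5 with Sections 3 and 8.2.4. Section 5.3 excludes only chronic use continuing after discharge, but the example in Section 5.5 could be read to remove any steroid user. The text should make clear whether women exposed around delivery stay in the analysis.

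Within-woman comparisons of mean glucose or time above 140 mg/dL, inside and after the window, would be an optional addition.

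The cost is a few sentences and one table from data already collected, with no added visits, participants or procedures. The downside is a wide interval that will show openly that the pilot does not settle the question.
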